6.9 Treatment exposure and compliance

Subjects will receive all study medication at the Investigator site. Study medication will be administered by site personnel, compliance will be ensured by appropriate training of site personnel. The date and time of administration of study drug will be recorded in the dosage administration record section of the eCRF.

Pharmacokinetic parameters (measures of treatment exposure) will be determined in all subjects treated with bimagrumab, as detailed in [Section 8.7](#).

6.10 Recommended treatment of adverse events

Muscle symptoms can be addressed with light self-massage of the involved area concentrating on improving circulation and relaxing muscle tissue. If excessive or prolonged soreness presents, then acetaminophen may be used as needed.

Acne may be treated with a face wash containing 4-10% benzoyl peroxide and over the counter topical treatments. If needed, a prescription topical treatment (i.e., antibiotics) or oral antibiotic (i.e., minocycline 100 mg bid) may be recommended at the Investigator's discretion. Early intervention is recommended when acne presents.

Diarrhea may be treated with over the counter remedies. In cases of prolonged occurrence, other treatments may be used at the Investigator's discretion.

Although not expected, any acute allergic reactions should be treated as needed using conventional counter measure therapies as indicated (including but not limited to epinephrine, antihistamine, corticosteroid, intravenous supplies, crystalloid, an oral airway, bag and mask, and supplemental oxygen). In the case of a serious adverse event in which decreasing the systemic concentration of bimagrumab may be of clinical benefit, the investigator should consider plasmapheresis. Study sites should not feel constrained in any way from providing necessary medical intervention.

Adverse events related to underlying disease of T2D: hypoglycemia or hyperglycemia events that are clinically significant based on the judgment of the principal investigator should be treated and managed according to local diabetes treatment guidelines and standard of care. Medication used to treat AEs must be recorded on the Concomitant medications/Significant non-drug therapies CRF.

Elevated lipase and amylase levels that meet AE criteria should be monitored and managed according to [Section 9.4](#).

6.11 Rescue medication

Not applicable.

6.12 Concomitant treatment

The investigator should instruct the subject to notify the study site about any NEW and changes to current medications he/she takes AFTER the start of the study.

All prescription medications, over-the-counter drugs and significant non-drug therapies (including physical therapy and blood transfusions) administered or taken within the timeframe defined in the entry criteria **prior to the start** of the study **and during** the study, must be recorded on the Concomitant medications/ Significant non-drug therapies section of the eCRF.

Should a subject have an *incidental and limited* need for a medication to be taken within the restricted *pre-dose* timeframe (e.g., ibuprofen for a headache, antibiotic prophylaxis prior to dental surgery, etc.), the sponsor should be advised, as administration of any concomitant medication *may* require the subject to be discontinued.

Administration of acetaminophen on an occasional basis is acceptable, but must be documented. Medication entries should be specific to trade name, the single dose and unit, the frequency and route of administration, the start and discontinuation date and the reason for therapy.

Medications allowed in the study as chronic therapy:

- Low dose aspirin is allowed.
- Oral anti-diabetic therapy (limited to metformin and/or DPP4 inhibitor agent), with stable treatment for approximately 3 months prior to randomization, for diabetes management during the trial. Insulin is allowed for one week only in case of acute deterioration of glycemic control.
- Stable regimen of testosterone replacement therapy for at least 3 months prior to randomization.
- Thyroid replacement therapy that is stable for at least 3 months prior to randomization.
- Antihypertensive medication must be on a stable regimen for at least 3 months prior to randomization.
- Medications for dyslipidemia must be stable for at least 3 months prior to randomization.
- Vitamin D and multivitamin/mineral supplementation (see below)
- Antidepressant medications must be stable for at least 3 months prior to randomization.
- Chronic therapy for hyperuricemia must be stable for at least 3 months prior to randomization.
- Other chronic therapy medications not listed above require Sponsor approval

6.13 Vitamin and mineral supplementation

- The subject must consume an oral multivitamin/multimineral supplement.
- In subjects with 25-OH vitamin D level between 12.0 and 50.0 ng/mL inclusive at screening:
 - Daily administration of vitamin D as part of the multivitamin/multimineral supplement (800 IU to 4000 IU, D3 preferable but D2 also acceptable per local availability); or,
 - Equivalent weekly or monthly formulation if deemed to be of advantage for the individual subject's compliance.
- In subjects with 25-OH vitamin D level \geq 50.0 ng/mL at screening: supplementation recommendations may be made at the investigator's discretion.
- In subjects with 25-OH vitamin D level $<$ 12.0 ng/mL at screening and with no symptoms of osteomalacia or low serum calcium: administration of loading dose of oral vitamin D (recommended minimum 50 000 IU of vitamin D3, but according to local guidance) will be allowed. Different formulations of vitamin D3 are allowed based on the approved therapy in the subject's country. Vitamin D2 is permitted where D3 is not available.

7 Study completion and discontinuation

7.1 Study completion and post-study treatment

Each subject will be required to complete the study in its entirety and thereafter no further study treatment will be made available to them. Study completion is defined as when the last subject completes their Study Completion visit, and any repeat assessments associated with this visit have been documented and followed-up appropriately by the Investigator, or in the event of an early study termination decision, the date of that decision.

If subjects discontinue early and are not able to return for their End of Treatment and End of Study visits, they should have a safety follow-up call conducted 30 days after the last dosing visit, per [Section 7.2](#). The information collected is kept as source documentation. All SAEs reported during this time period must be reported as described in [Section 9.2](#) and the Site Operations Manual. Documentation of attempts to contact the subject should be recorded in the source documentation.

7.2 Discontinuation of study treatment

Subjects may voluntarily discontinue study treatment for any reason at any time.

The investigator must discontinue study treatment for a given subject if, on balance, he/she believes that continuation would be detrimental to the subject's well-being.

Study treatment *must* be discontinued for an individual subject under the following circumstances:

- Withdrawal of consent
- An infusion reaction that is considered severe
- One or more symptomatic hypoglycemic events necessitating third party rescue and suspected to be related to study drug; if diabetes medication can be appropriately reduced, the study drug may be resumed after stabilization of FPG at the Investigator's discretion
- A serious adverse event (SAE) thought to be related to study drug
- Pregnancy: a positive urine pregnancy test after start of study treatment requires immediate interruption of study treatment until serum hCG is performed and found to be negative
- Any protocol deviation that results in a significant risk to the subject's safety
- Emergence of one or more adverse events that in the judgment of the investigator, taking into account the subject's overall status, prevent the subject from safely continuing in the study

Investigational treatment *may* be discontinued under the following circumstances:

- Breaking of the blind (inadvertently or for emergency reasons)
- Use of prohibited treatment as described in the protocol

Subjects who discontinue study treatment should **NOT** be considered withdrawn from the study UNLESS they withdraw their consent. They should return approximately 4 weeks after their last dose for the EoT visit (Visit 113). The EoS visit (Visit 199) should be scheduled

4 weeks after EoT. If they fail to return for these assessments for unknown reasons, every effort should be made to contact them as specified in [Section 7.4](#).

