After completion of the treatment period, subjects will have a follow-up period of 8 weeks with regular monitoring for safety and efficacy beginning at Week 48 and continuing until the end of study visit (EOS) which will take place 12 weeks after the last study drug administration. The specific assessments for the follow up and end of study visits are detailed in [Section 8.1](#) (Assessment schedule).

Figure 3-1 Study design

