3.7.3 Blood sample volumes

A maximum of 500 mL of blood is planned to be collected from each subject during the study over a period of 392 days (56 weeks). Additional samples for monitoring of any safety findings are not included. Blood collection is not considered to be a risk for this population.

During the collection of blood samples, subjects may experience pain and/or bruising at the insertion site of the needle/catheter. Although rare, localized clot formation, infections and nerve injury may occur. Lightheadedness and/or fainting may also occur during or shortly after the blood draw. Patients will be observed following all blood draws and discharged only when the Investigator observes stable health status. In addition, liquids by mouth in the form of water, fruit juice or a similar product will be provided following the blood draw to replenish the blood volume removed.

Timings of blood sample collection are outlined in the Assessment Schedule, [Section 8.1](#). A summary blood log is provided in the Site Operations Manual, together with instructions for all sample collection, processing, storage and shipment information.

See [Section 8.9](#) regarding the potential use of residual samples.

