9.1 Adverse events

An adverse event (AE) is any untoward medical occurrence (i.e., any unfavorable and unintended sign [including abnormal laboratory findings], symptom or disease) in a patient or clinical investigation patient after providing written informed consent for participation in the study until the end of study visit. Therefore, an AE may or may not be temporally or causally associated with the use of a medicinal (investigational) product.

In addition, all reports of intentional misuse and abuse of the study treatment are also considered an AE irrespective if a clinical event has occurred. See [Section 9.6](#) for an overview of the reporting requirements.

The occurrence of AE must be sought by non-directive questioning of the patient at each visit during the study. AEs also may be detected when they are volunteered by the patient during or between visits or through physical examination finding, laboratory test finding, or other assessments.

Abnormal laboratory values or test results constitute AEs only if they fulfill at least one of the following criteria:

- they induce clinical signs or symptoms,
- they are considered clinically significant,
- they require therapy.

Clinically significant abnormal laboratory values or test results should be identified through a review of values outside of normal ranges/clinically notable ranges, significant changes from baseline or the previous visit, or values which are considered to be non-typical in patients with underlying disease. Investigators have the responsibility for managing the safety of individual patients and identifying AEs. Alert ranges for liver and kidney related events are included in [Appendix 1](#) and [Appendix 2](#), respectively. Other laboratory values to check are markers of muscle distress (CK, myoglobin) and pancreatic enzymes (amylase and lipase).

AEs must be recorded on the Adverse Events CRF under the signs, symptoms or diagnosis associated with them, and accompanied by the following information:

1. The severity:
 - mild: usually transient in nature and generally not interfering with normal activities
 - moderate: sufficiently discomforting to interfere with normal activities
 - severe: prevents normal activities
2. Its relationship to the study treatment:
 - Yes or
 - No
3. Its duration (start and end dates) or if the event is ongoing, an outcome of not recovered/not resolved must be reported.

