11.7 Sample size calculation

A sample size of 68 recruited subjects (34 receiving active treatment and 34 placebo) is selected to enable at least 48 completers, assuming a dropout rate of maximum 30%.

A sample size of 24 completers per group (total of 48 patients) provides about 70% power (see [Table 11-1](#)) to pass the criteria described above for fat mass (significant reduction at the 1-sided 10% level (compared to placebo) and an estimated median placebo-adjusted reduction of at least 5%). Assumptions used for these calculations include a true placebo-adjusted fat loss of 6% (standard deviation 6.5%, CBYM338X2206). The associated type I error is about 1% ([Table 11-1](#)).

Because weight loss interventions in overweight/obese diabetic patients result in ~ 15% lower magnitude of response compared to overweight/obese non-diabetic patients ([Franz et al 2007](#)), we made the assumption that bimagrumab could have a 6% true effect on fat loss in overweight and obese diabetic patients (this is about 15% lower than the 7.2% effect observed in overweight and obese pre-diabetics (CBYM338X2206)).

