### **Adverse events**

All information obtained on adverse events will be displayed by treatment and subject.

The number and percentage of subjects with adverse events will be tabulated by body system and preferred term with a breakdown by treatment. A subject with multiple adverse events within a body system is only counted once towards the total of this body system and treatment.

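### Adverse events are observed for 8 to 48 weeks in early stoppers and 56 weeks in completers but summarised only as crude percentages, which can distort the between-arm picture in either direction if stopping differs by arm

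*Protocol*

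**What the plan says.** Protocol 7.2 keeps patients who stop treatment in the study unless they withdraw consent, but brings their closing visits forward. For end of treatment, "They should return approximately 4 weeks after their last dose for the EoT visit (Visit 113"); the end-of-study visit is then set "4 weeks after EoT". That is about 8 weeks after the last dose. Under Protocol 7.1, early stoppers who cannot attend those visits are followed by telephone: "they should have a safety follow-up call conducted 30 days after the last dosing visit".

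Completers follow a longer path. Protocol 3.1 describes "the end of study visit (EOS) which will take place 12 weeks after the last study drug administration", and Protocol 3.7.3 gives the whole span as "over a period of 392 days (56 weeks").

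Protocol 9.1 counts adverse events from consent for participation in "the study until the end of study visit", so the collection window closes when the individual patient's end-of-study visit takes place.

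On analysis, SAP 7.2 states: "The number and percentage of subjects with adverse events will be tabulated by body system and preferred term with a breakdown by treatment". Protocol 11.5.2 says the same. The safety set (Protocol 11.1, SAP 4) is everyone who received any study drug. No patient-time rate, time-to-event summary, common cut-off or display of observation time appears in the adverse event text. The separate heading for other safety evaluations is redacted in both documents, so nothing can be said about what it contains.

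Protocol 11.7 sizes the study "assuming a dropout rate of maximum 30" per cent, with no figure per arm.

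**The concern.** A crude percentage treats a patient watched for 8 weeks and a patient watched for 56 weeks as equally informative. If the two arms have the same pattern of early stopping, the shortfall is shared and cancels between arms, although each percentage still understates what full follow-up would have shown. If the patterns differ, part of any difference in the table, or part of any reassuring similarity, comes from unequal observation and not from the drug.

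Safety and tolerability is a stated secondary objective, and the study exists to support development decisions. Dropout of up to 30% is allowed for, and some of the mandatory stopping reasons in Protocol 7.2 are tied to study drug, so unequal stopping is a realistic possibility. A reader who has only the crude percentages cannot tell whether it has affected them, or in which direction.

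**Working it through.** **Inputs from the documents.** Twelve doses, one every 4 weeks (Protocol 6.2), so dose *k* falls at Week 4(*k* − 1) and dose 12 at Week 44 (Day 308 / 7). Early stopper: end of study 4 + 4 = 8 weeks after the last dose (Protocol 7.2). Completer: end of study 12 weeks after dose 12, which is Week 44 + 12 = 56 (392 / 7 = 56). Planned size 34 per arm. The plan's only calculation that uses dropout reproduces to rounding: 68 × 0.70 = 47.6, against the stated 48 completers.

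**Observation windows.** For a last dose number *k* from 1 to 11, the window is 4(*k* − 1) + 8 weeks:

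| Last dose | Window (weeks) | Short of Week 56 by |
|---|---|---|
| 1 | 8 | 48 |
| 3 | 16 | 40 |
| 6 | 28 | 28 |
| 9 | 40 | 16 |
| 11 | 48 | 8 |
| 12 (completer) | 56 | 0 |

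The mean over *k* = 1 to 11 is 28 weeks. Off-drug follow-up is 8 weeks for stoppers and 12 for completers.

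**Assumptions, because the documents give no figure.** True 56-week incidence *p*; constant hazard, equal in both arms, that continues at the same level after a stop; share of early stops *d* in each arm; stops spread evenly over doses 1 to 11 and unrelated to adverse events; every stopper attends the end-of-study visit.

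**Formula.** λ = −ln(1 − *p*) / 56. Crude percentage = (1 − *d*) × *p* + *d* × *m*, where *m* is the mean over *k* of 1 − exp(−λ × window).

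**Scenario 1, stops unrelated to events.** Take *p* = 40%: λ = 0.00912 per week and *m* = 22.0%.
- *d* = 20%: 0.8 × 40 + 0.2 × 22.0 = 36.4%; mean window 0.8 × 56 + 0.2 × 28 = 50.4 weeks.
- *d* = 40%: 0.6 × 40 + 0.4 × 22.0 = 32.8%; mean window 0.6 × 56 + 0.4 × 28 = 44.8 weeks.
- Gap 3.6 points; 0.036 × 34 = 1.2 patients.

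The 20% v 40% split averages to the planned 30%. Other settings:

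| True incidence | Stops | Crude % |
|---|---|---|
| 20% | 20% v 40% | 18.1 v 16.2 |
| 40% | 10% v 50% | 38.2 v 31.0 |
| 10% | 10% v 30% | 9.5 v 8.5 |
| 50% | 10% v 30% | 47.8 v 43.5 |
| 50% | 10% v 30%, all after doses 1 to 3 | 46.4 v 39.1 |
| 40% | 30% v 30% | 34.6 v 34.6 |

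**Scenario 2, the extra stops are themselves counted events.** Keep *p* = 40% and 20% v 40% stops, but let the extra 20 points in the second arm each be caused by an event already in the table: 0.2 × 100 + 0.2 × 22.0 + 0.6 × 40 = 48.4%, against 36.4%. With *p* = 30% and 10% v 30% stops, the same reasoning gives 42.6% v 28.6%. Now the arm with more stops looks less safe.

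**Does the fix remove the artefact in Scenario 1?** Under equal constant hazards, first events divided by time at risk estimate λ in each arm whatever *d* is. For *p* = 40% that is 0.00912 × 52 = 0.47 per patient-year in both arms.

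**The case against.** - **Direction.** A reader might infer that the arm with more early stops will look safer. The documents do not support that as a general statement. It needs unequal stopping, which the plan neither predicts nor quantifies by arm; stops largely unrelated to counted events; and events that keep accruing. Protocol 7.2 makes severe infusion reactions, drug-related serious events, hypoglycaemia needing third-party rescue and intolerable adverse events mandatory grounds for stopping. Those patients are already in the numerator, and Scenario 2 shows the reversal. This objection stands, and the point is limited accordingly.
- **Lost time is mostly off drug.** Eight weeks after the last dose matches the wash-out of about 8 weeks given in Protocol 3.3. Extending a stopper's hazard unchanged to Week 56 is a hypothetical yardstick. This also stands in large part. The table would still pool patients with 1 to 11 doses and those with 12 without showing it.
- **Constant hazard.** Protocol 3.7.2 reports spasms in all six subjects given three 10 mg/kg infusions. For events that come this early, a later stop loses little, and a per-patient-year rate can mislead the other way by dividing by a shorter time in the arm with more stops. This stands, and it limits how the rate should be used.
- **Size.** In the main illustration the gap is 1.2 patients of 34. The sampling standard error of that difference is √(0.364 × 0.636 / 34 + 0.328 × 0.672 / 34) ≈ 11.5 points, about three times the artefact. The trial is non-confirmatory and no formal comparison of adverse events is planned.
- **Existing safeguards.** Dated events and dosing are listed by patient. Serious events run to 30 days after the last visit, and later if suspected to be related. Patients are asked to report possibly related events afterwards, an independent committee reviews unblinded safety data, and SAP 7.3 permits figures. These help, but none puts a summary by arm that allows for observation time into the planned tables.

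One simplification works in the other direction. Patients who withdraw consent have no further assessments (Protocol 7.3), and those who cannot return get a call at 30 days, so some windows are shorter than assumed here.

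**Conclusion.** The point holds in a conditional form. That windows differ, at about 8 to 48 weeks against 56, follows directly from the visit rules, and the unredacted adverse event analysis makes no allowance for it. With equal stopping there is no between-arm artefact. With unequal stopping the crude percentages can mislead, and the direction depends on why patients stop.

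For stops unrelated to events, the artefact is about 1 to 4 points at 10% v 30% stopping spread evenly, for true incidences of 10% to 50%. It is 3.6 points in the 20% v 40% illustration, and up to about 7 points if stops cluster after doses 1 to 3. All of these rest on assumed stopping shares by arm, equal constant hazards and attendance at the closing visits. The effect is small beside sampling error in a study of this size, so this is a worthwhile and inexpensive improvement, not a serious flaw.

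**What to change.** In SAP 7.2, under adverse events, keep n (%) and add:

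1. Adverse event observation time by arm (median and total patient-years, first dose to end-of-study visit) in the table header.
2. Patients with a first event per patient-year by arm, counting time from first dose to first event or end of study, with the rate difference and its confidence interval.
3. Time-to-first-event curves by arm to Week 56 for the events of special interest named in Protocol 9.1 (painful spontaneous muscle contractions and diarrhoea).

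No visit, dose or data collection changes; event, dosing and visit dates are already recorded. The cost is SAP wording, extra table columns and a few figures. The downside is that the rate assumes a roughly constant hazard and can mislead for early-onset events, while the curves assume that censoring is non-informative, which event-driven stopping would breach. Both should therefore stand beside the crude percentages and not replace them.

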A capped dose for these subjects is selected to avoid over-exposure and to maintain bimagrumab levels around the threshold for safe anabolic effects over 4-week dosing intervals. Specifically, the selected amount of 1200 mg translates to a body weight based dose ranging from 10 to 8.6 mg/kg for the body weight range of 120-140 kg, which is predicted to result in exposure levels within the safe and efficacious range for bimagrumab and with minimal risk of over-exposure.

Rationale for duration of treatment

A treatment duration of 48 weeks is selected to capture the temporal profile as well as maximal effect of bimagrumab on body fat mass. While a ceiling effect is typically observed on lean mass gain with bimagrumab, the loss of fat mass does not seem to plateau over a period of 24 weeks and even up to 64 weeks (Internal data).

Rationale for follow-up period

An off-drug follow-up period is included to monitor the durability of treatment effect of bimagrumab on body fat mass, lean mass and glycemic control once off treatment. The EOS visit being performed 12 weeks after the last administration covers the wash-out period of bimagrumab exposure associated with anabolic effect (approximately 8 weeks).

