In early studies, a smaller percentage of muscle symptoms were seen in older healthy volunteers 70-83 years of age than in young and middle aged adults. A case of spasm was reported by one subject (of 6) that received 3 mg/kg, while no cases were reported in the group receiving 30 mg/kg.

The etiology and clinical meaning of these observations are not known. Similar symptoms have been reported with at least one other anabolic molecule, a beta-2 adrenergic agonist (Tomlinson et al 1990) and are commonly reported by adults performing muscle building exercise. Data on twitches and the effects on people receiving bimagrumab are detailed in the Investigator's Brochure.

Table 3-2 Muscle symptoms considered possibly related to bimagrumab from unblinded data*

Company Confidential Information

Company Confidential Information

Reproductive organs

Data from CBYM338X2108 demonstrate no clinically or statistically significant effect of bimagrumab on circulating testosterone levels and no effect on the pituitary-gonadal or pituitary-adrenal axes in either gender. Suppression of FSH levels in postmenopausal women and premenopausal women of non-childbearing potential has been observed with no associated safety risk identified. All effects were transient and resolved after bimagrumab exposure ended. Semen analysis data from the multiple dose study suggest that three doses of 10 mg/kg have no effect on sperm count or quality in males.

Women of childbearing potential may participate in this study as long as they use highly effective contraception as detailed in [Section 4.2](#) (Exclusion criteria).

Immunogenicity

It is possible that anti-drug antibodies could develop against bimagrumab, which could neutralize or clear the drug more rapidly and attenuate its efficacy. A treatment related anti-drug antibody response has been observed in subjects treated with bimagrumab although it should be noted that high exposure to bimagrumab may mask the presence of an immune response. Nevertheless, there was no evidence of an infusion or hypersensitivity reaction that could be related to immunogenicity or any sign of immune complex formation in the clinical trials performed so far. No positive signal in the immunogenicity assay was accompanied by a change in the bimagrumab PK profile.

Lipase and amylase elevations

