9.2.2 SAE reporting

To ensure patient safety, every SAE, regardless of causality, occurring after the patient has provided informed consent and until 30 days after the last study visit must be reported to Novartis **within 24 hours of learning of its occurrence** as described below. Any SAEs experienced after this period should only be reported to Novartis if the investigator suspects a causal relationship to study treatment.

Note: SAEs reported by patients deemed to be screen failures must be reported to Novartis as outlined here with appropriate information also captured in the CRFs as specified in the Site Operations Manual.

Recurrent episodes, complications, or progression of the initial SAE must be reported as follow-up to the original episode, regardless of when the event occurs. This report must be submitted within 24 hours of the investigator receiving the follow-up information. An SAE that is considered completely unrelated to a previously reported one should be reported separately as a new event.

Information about all SAEs (either initial or follow up information) is collected and recorded on the paper SAE Report Form. The investigator must assess the relationship to each specific component of study treatment (if study treatment consists of several drugs) complete the SAE Report Form in English, and send the completed, signed form by fax within 24 hours after awareness of the SAE to the local Novartis Drug Safety and Epidemiology Department,

notifying the Clinical Trial Leader. Contact information is listed in the Site Operations Manual.

The original copy of the SAE Report Form and the fax confirmation sheet must be kept with the source documentation at the study site. Follow-up information should be provided using a new paper SAE Report Form stating that this is a follow-up to a previously reported SAE.

SAEs (initial and follow-up) that are recorded electronically in the Electronic Data Capture system should be entered, saved and e-signed within 24 hours of awareness of the SAE or changes to an existing SAE. These data will automatically be submitted to Novartis Drug Safety & Epidemiology immediately after investigator signature or 24 hours after entry, whichever occurs first. Study site personnel must also inform the Clinical Trial Leader.

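### Subjects who stop treatment early have their end-of-study visit 8 weeks after the last dose, not the 12 weeks given in Sections 3.1 and 3.3, and no reason is stated

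*Protocol*

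**What the plan says.** Protocol 7.2 gives one visit rule for every subject who discontinues study treatment without withdrawing consent: "They should return approximately 4 weeks after their last dose for the EoT visit (Visit 113). The EoS visit (Visit 199) should be scheduled", and the sentence continues "4 weeks after EoT. If they fail to return for these assessments for unknown reasons". The mandatory stops in the same section include severe infusion reactions, SAEs thought to be drug-related, and adverse events that make it unsafe to continue. Visit 114 is not mentioned for these subjects.

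Elsewhere the interval is longer. Section 3.1 describes "the end of study visit (EOS) which will take place 12 weeks after the last study drug administration". Section 3.3 gives the reason: "The EOS visit being performed 12 weeks after the last administration covers the wash-out period of bimagrumab exposure", with that wash-out put at approximately 8 weeks. Table 8-1 agrees for completers: last dose on Day 308 (Visit 112), EoT on Day 336 (Visit 113), a follow-up visit on Day 364 (Visit 114) and EoS on Day 392 (Visit 199).

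The timing of EoS fixes several collection windows. Section 9.1 defines adverse events as those occurring "after providing written informed consent for participation in the study until the end of study visit". Section 9.2.2 requires every SAE, regardless of causality, occurring "until 30 days after the last study visit must be reported to Novartis". Table 8-1 places the final PK and immunogenicity samples at EoS.

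**The concern.** A wash-out runs from the last dose, whether that is the third or the twelfth. If 12 weeks is the interval chosen so that EoS clears an exposure period of about 8 weeks, the same argument applies to a subject who stops early. Under 7.2 the EoS visit falls at the end of that approximate period, with no margin, and the protocol does not say why.

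The shorter interval falls on the subjects of most safety interest. New non-serious events are collected for a shorter time after their last dose. Their last antibody sample is also taken earlier, although Section 3.7.2 warns that "high exposure to bimagrumab may mask the presence of an immune response". After a severe infusion reaction, a later sample with less drug on board is the more informative one.

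**Working it through.** This is date arithmetic on the visit schedule.

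**Inputs**
- Completers (Table 8-1): last dose Day 308, EoT Day 336, EoS Day 392.
- Early stoppers (7.2): EoT about 28 days after the last dose, EoS 28 days after EoT.
- Exposure wash-out (3.3): about 8 weeks, or 56 days.
- SAE reporting (9.2.2): last visit + 30 days.
- Enrolment and dropout (11.7): 68 recruited, at least 48 completers, dropout at most 30%.
- SAP 6.1.3.1: EOS within 8 weeks ± 10 days of the Week 48 assessment, and no early discontinuation.

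**The plan's own figure.** Last dose to EoS for completers is 392 − 308 = 84 days = 12 weeks. This is 336 − 308 = 28 days to EoT plus 392 − 336 = 56 days to EoS, and it matches 3.1 and 3.3.

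**The same interval under 7.2.** 28 + 28 = 56 days = 8 weeks.

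| Quantity (days after last dose) | Completer | Early stopper | Difference |
|---|---|---|---|
| EoS; end of new AE collection | 84 | 56 | 28 |
| Margin beyond a 56-day wash-out at EoS | 84 − 56 = 28 | 56 − 56 = 0 | 28 |
| SAE reporting, any causality | 84 + 30 = 114 | 56 + 30 = 86 | 28 |
| Last PK and antibody sample | 84 | 56 | 28 |

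The 28 days are 28/84 = one third of the off-drug window and 28/56 = half of the follow-up after EoT. Section 7.2 says only approximately 4 weeks for EoT. Assuming that visit moves by ± 7 days, EoS falls at 21 + 28 = 49 to 35 + 28 = 63 days, and the shortfall is 35 to 21 days.

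**How many subjects.** 68 − 48 = 20 (30% of 68 is 20.4). With an even split, which is an assumption, about 10 are on bimagrumab. The number is smaller if some withdraw consent or do not return.

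**Effect of a correction on the SAP window.** 56 ± 10 gives 46 to 66 days from EoT to EoS. The present 28-day gap of an early stopper lies outside this window. A corrected 56-day gap would lie inside it.

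**The case against.** The strongest reply is that little is lost. The affected window is Days 57 to 84 after the last dose, and SAE reporting regardless of causality runs to Day 86, so it covers the whole window. After that, SAEs suspected to be related stay reportable. Adverse events already detected are followed until resolved or judged permanent, and later events thought related go into source documents (9.1). All of this stands. A reader might infer that early stoppers go unobserved for 28 days; the documents do not support that. The loss is limited to scheduled visits, database capture of new non-serious events, and the timing of the final samples.

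A reader might also call this a contradiction between 3.1 and 7.2. The 3.1 text concerns subjects who have completed the treatment period, so 7.2 can stand as a separate rule. The rationale in 3.3 concerns durability of effect and exposure associated with anabolic effect, so extending it to safety stops is an inference. It is a reasonable one, because 3.3 is not restricted to completers and no other reason is offered for 8 weeks.

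On immunogenicity, 3.7.2 also reports no infusion or hypersensitivity reaction attributable to it so far, and no positive assay signal accompanied by a change in PK. That lowers the expected yield of a later sample but does not remove the masking problem.

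Two larger size claims do not hold. Multiplying 20 × 28 = 560 subject-days and calling them lost wash-out cover counts placebo subjects, who have no drug to wash out. And the interval is not what chiefly affects crude AE percentages by arm. A subject whose last dose is on Day 112 has EoS on Day 112 + 56 = 168, which is 392 − 168 = 224 days before a completer's; the correction recovers 28 of those.

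**Conclusion.** The point holds in a limited form. Early stoppers have EoS 56 days after the last dose against 84 for completers, without a stated reason. The consequence is 28 fewer days of scheduled collection of new non-serious adverse events, and final PK and antibody samples at week 8 instead of week 12. At the planned maximum dropout this concerns at most about 20 of 68 subjects, about 10 on active drug. That count assumes the 30% ceiling is met, an even split between arms, and that all of them return.

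A reader might infer that the primary Week 48 result is affected. It is not: Protocol 11.4.1 and SAP 6.1.1 already exclude EoT assessments of subjects who discontinued early. The documents give no rate for late-onset events, so no number of missed events can be stated. The change is worth making because it is cheap and concerns subjects stopped for safety, but it is not critical to the trial's conclusions.

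**What to change.** In Protocol 7.2, schedule EoS 8 weeks after EoT, which is 12 weeks after the last dose.

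Moving EoS alone would remove the only visit at 8 weeks after the last dose and leave early stoppers with nothing between weeks 4 and 12. Completers have Visit 114 at that point (364 − 308 = 56 days). So keep a contact at 8 weeks, either Visit 114 as it exists or a telephone adverse-event check.

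In SAP 6.1.3.1, keep the condition that the subject did not discontinue early as the operative filter. Once the EoT-to-EoS gap is 56 days, the 8 weeks ± 10 days window no longer separates early stoppers from completers.

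Cost: a protocol amendment under 13.1, EoS 28 days later, and one light visit or call, for at most about 20 subjects. Subjects who cannot return are not helped; they keep the 30-day safety call of 7.1.
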